8.1.2 Part 2, M8891 with Cabozantinib, mRCC

8.1.2.1 Part 2A, Dose Escalation

In Part 2A, a Bayesian model is applied to assist the SMC in dosing decisions. For details on the model see Section 8.5.3. Like Part 1, the sample size for the dose escalation in Part 2A cannot be exactly prespecified but depends among other things on the number of DLTs seen. The planned cohort size is 3 subjects. The SMC may decide to change the planned cohort size. The total sample size will depend on the number of cohorts to be evaluated. It is anticipated that 6 to 15 subjects maximum will be needed. The following scenario is possible: 2 dose levels with 3 subjects each and 1 dose level with 6 subjects, resulting in 12 subjects.

8.1.2.2 Part 2B, Expansion Cohort

In the Part 2B expansion cohort, a 2-stage design with a total of 30 subjects evaluable for response will be applied. If 11/30 responses are seen at the final analysis, the posterior probability that the ORR $\geq 30\%$ is 81%.

An interim analysis for futility will occur after enrollment of 15 subjects treated at the same dose who are evaluable for response. The cut-off for the interim analysis for futility was chosen to balance sufficient information for decision with the potential of sparing subjects an additional treatment from the standard of care cabozantinib. The boundary and operational characteristics are described in Section 8.5.2

In case the SMC decides to decrease the M8891 dose during the expansion phase, then only subjects treated at the same dose will be considered in the 2-stage design. Therefore, the number of subjects in the expansion cohort might increase to reach the required number of 30 subjects treated on the same dose who are evaluable for response. The increase in sample size is limited to maximally 40 subjects in Part 2B.

8.2 Randomization

Not applicable.

8.3 Endpoints

8.3.1 Part 1, M8891 Single Agent, Solid Tumors

8.3.1.1 Primary Endpoints

The primary endpoint of the Part 1 of this trial is DLTs during the first 21-day treatment cycle, based on a predefined set of AEs, to determine the MTD.

8.3.1.2 Secondary Endpoints

Secondary endpoints include:

- Occurrence and severity of TEAEs, and deaths, including cause of death, from screening up to the End of Treatment Visit
- Changes in clinical laboratory measures, ECG measures, vital signs, ECOG PS
- PK parameters of M8891 after QD dosing:
 - C_{max} , t_{max}
 - AUC_{0-t} ,
 - $AUC_{0-\infty}$,
 - $AUC_{0-\tau}$,
 - $t_{1/2}$,
 - λ_z ,
 - CL/F ,
 - CL_{ss}/F ,
 - V_z/F ,
 - $Racc(AUC_{\tau})$
 - $Racc(C_{max})$

Time points for PK assessments for QD dosing: Cycle 1 Day 1: 0 hour (pre-dose within 60 minutes prior to each treatment administration) and 1 (± 10 minutes), 2 (± 10 minutes), 3 (± 10 minutes), 4 (± 20 minutes), 5 (± 20 minutes), 6 (± 30 minutes), 8 (± 30 minutes), 12 hours post-dose (± 60 minutes), on Day 2 at 24 hours post-dose (before next drug administration) (± 60 minutes). Cycle 1 Day 8: 0 hour (pre-dose within 60 minutes prior to treatment administration), Cycle 1 Day 15: 0 hour (pre-dose within 60 minutes prior to each treatment administration) and 1 (± 10 minutes), 2 (± 10 minutes), 3 (± 10 minutes), 4 (± 20 minutes), 5 (± 20 minutes), 6 (± 30 minutes), 8 (± 30 minutes), 12 hours post-dose (± 120 minutes), on Day 16 at 24 hours post-dose (before next drug administration) (± 60 minutes), 63 mL blood in Cycle 1. Cycle ≥ 2 Day 1: 0 hour (pre-dose within 60 minutes prior to each treatment administration).

- Best overall response (BOR: CR, PR, SD, or PD) according to RECIST v 1.1. criteria as assessed by Investigators
- Clinical benefit defined as CR, PR, or SD for ≥ 12 weeks
- PFS is defined as the time from first study drug administration to either first observation of PD (as assessed by RECIST v 1.1) or occurrence of death due to any cause, whichever occurs first.

8.3.1.3 Other Endpoints

CCI

8.3.2 Part 2, M8891 with Cabozantinib, mRCC

Endpoints for Part 2A are provided in Table 6 and endpoints for Part 2B are provided in Table 7.

8.4 Analysis Sets

For purposes of analysis, the following populations are defined in Table 13.

Table 13 **Analysis Sets**

Population	Description
Screening	All subjects who sign informed consent
Dose Escalation	All subjects treated in dose escalation cohorts who either Part 1: 
• did not miss > 4 cumulative days of planned doses of M8891 in the first cycle of the dose escalation part or• who experienced a DLT Part 2A and 2B: 
• Received at least 80% of the planned cumulative dose of each treatment in the first cycle of the dose escalation part or• who experienced a DLT
Safety	The Safety Analysis Set will include all subjects who receive at least one dose of trial treatment.
Pharmacokinetic	All subjects from the safety analysis set without major protocol deviations/violations or events that would affect PK. Subjects in the PK analysis set must have received at least 1 dose of M8891, and M8891 combined with cabozantinib and have sufficient M8891/cabozantinib plasma concentration data to enable the calculation of at least one PK parameter. Sufficient concentration data is defined as at least 3 valid, post-dose concentration points in the PK profile to obtain any PK parameter.
Pharmacodynamics in WBCs	All subjects who received at least one dose of M8891 and provide the pre-dose and at least one post-dose WBC assessment. (Only for Part 1 of the study.)
CC1	

PK: Pharmacokinetic; WBC: White blood cell.

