5.1.3.1 Part 1, M8891 Single Agent, Solid Tumors

The treatment period will begin at the first dose of M8891 in Cycle 1 Day 1 and consist of consecutive 21-day cycles of continuous once daily M8891 monotherapy under fasting conditions.

Subjects will receive M8891 at the pre-specified dose level until disease progression, unacceptable toxicity, withdrawal of consent, or any criterion for withdrawal from the study (Section 5.5.2).

If the subject tumor evaluation indicates that the disease is slowly progressing according to the CT scan as per Response Evaluation Criteria in Solid Tumors (RECIST) v1.1 criteria (a growth of the target lesions of less than 35% from baseline and no new lesions, or new lesion(s) smaller than 1 cm; bone metastatic lesions or lesions treatable with local radiotherapy would also fall in the same category), but the subject performance status is the same as baseline and there are no safety concerns, i.e. no ongoing symptomatic events Grade 2 or higher in severity, treatment may be continued for another 2 cycles to the next tumor evaluation, upon evaluation by the treating physician and after the continuation of therapy has been discussed with the Sponsor.

CCI

In principle, dose escalation of M8891 will proceed according to the decision of the SMC to the MTD, or the SMC may decide ceasing further dose escalation following review of safety, tolerability, PK and CC results.

The selection of the recommended dose for the expansion cohort of M8891 is based on the following criteria derived from the PK/C_{max} model:

CCI

The MS100015-0019 trial employs a Bayesian two-parameter logistic regression model with overdose control to assist the SMC with dose selection (Babb 1998; Neuenschwander 2008). The model incorporates nonclinical toxicity and observed DLT information from all previously completed dose escalation cohorts to provide a dose recommendation for the next dose cohort. The SMC will decide on the next dose level based on the Bayesian model, safety, PK analyses CCI [REDACTED] Dose escalation will start at 7 mg administered once daily.

A preselected set of doses (8 projected escalation steps with doses of 7, 12, 20, 35, 60, 100, 150 and 210 mg QD) are considered by the model, although doses may be skipped and/or others that are not part of the pre-specified set may be chosen as well. Sequential cohorts of 3 subjects at the same dose level will be used.

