8.1 Sample Size

8.1.1 Part 1, M8891 Single Agent, Solid Tumors

A Bayesian model is applied to assist the SMC in dosing decisions. For details on the model see Section 8.5.3.1

As this is the dose escalation part of the trial, with M8891 single agent, sample size cannot be exactly prespecified, but depends among other things on the number of DLTs seen.

The sample size for Part 1 dose escalation (QD) is capped at a maximum of 42 subjects.

At least 6 subjects need to have been treated at the suggested MTD or RP2D. That might necessitate the enrollment of additional subjects after dose escalation was stopped. For this sample size assessment, it is assumed that it is not necessary to enroll additional subjects to fulfill this criterion.

It is anticipated that 36 evaluable subjects (8 dose levels with 3 to 12 subjects, e.g. assuming a scenario with 5 dose levels with 3 subjects, 2 dose levels with 6 subjects (2 cohorts) and one dose level with 9 subjects (3 cohorts) may be needed in order to determine the MTD of QD dosing of M8891.

The anticipated total number of evaluable subjects is approximately 36 (42 if the maximal sample size stopping criterion is reached).

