8.5.4 Pharmacokinetics

8.5.4.1 Descriptive Statistics

The PK variables will be analyzed descriptively for each dose level and day, separately. Descriptive statistics for PK concentrations are: number of non-missing observations (N), arithmetic mean (Mean), standard deviation, coefficient of variation (CV%), minimum, median and maximum. Descriptive statistics of PK Parameters should additionally show the geometric mean, the geometric coefficient of variation and the 95% confidence interval for the geometric mean. The drug concentration in plasma at each sampling time will be presented on the original scale for all subjects in the PK analysis set. Values below the LLOQ will be taken as zero for descriptive statistics of concentrations.

Individual plasma concentration-time profiles (linear and semi-logarithmic scale) will be plotted. Mean plasma concentrations per dose level and day will be plotted with standard deviation using scheduled time points. If evidence is given that the weight affects the PK parameters, the analyses will also be performed for weight normalized PK parameters.

All statistical tests will be performed in an exploratory way.

All analyses will be based on the PK data set.

Details of the statistical analyses will be described in the Integrated Analysis Plan.

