M8891 concentration data will be descriptively summarized using: number of non-missing observations (N), arithmetic mean (Mean), standard deviation (Sd), coefficient of variation (CV%), minimum (Min), median (Median) and maximum (Max). If there are fewer than 3 observations, only N, Min, and Max will be reported.

Descriptive statistics of PK concentration data will be calculated using values with the same precision as the source data, and rounded for reporting purposes only. The following conventions will be applied when reporting descriptive statistics of PK concentration data:

Mean, Min, Median, Max: 3 significant digits
Sd: 4 significant digits
CV%: 1 decimal place

Presentation of PK parameter data

Pharmacokinetic parameter data will be descriptively summarized using: number of non-missing observations (N), arithmetic mean (Mean), standard deviation (Sd), coefficient of variation (CV%), minimum (Min), median (Median), maximum (Max), geometric mean (GeoMean), the geometric coefficient of variation (GeoCV%) and the 95% confidence interval for the GeoMean (LCI 95% GM, UCI 95% GM). For time to reach maximum observed concentration (t_{max}), only N, Min, Median and Max will be reported.

The PK parameter maximum observed plasma concentration (C_{max}) will be reported with the same precision as the source data and t_{max} will be reported to 2 decimal places. All other PK parameters will be reported to 3 significant figures. In export datasets, as well as in the Study Data Tabulation Model (SDTM) PP domain, PK parameters will be provided with full precision, and will not be rounded. Descriptive statistics of PK parameter data will be calculated using full precision values, and rounded for reporting purposes only.

The following conventions will be applied when reporting descriptive statistics of PK parameter data:

Mean, Min, Median, Max, GeoMean, 95% CI: 3 significant digits Sd: 4 significant digits CV%, GeoCV%: 1 decimal place

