Data will be further analyzed using concentration effect modeling for baseline corrected QTcF values. Change from baseline (QTcF) will be modelled using a linear mixed model, with baseline QTcF value and drug concentration as continuous covariates, and subject as a random factor, using data from the first cycle, and additionally using all data until cut-off. One model will be run using an unstructured covariance matrix, another one using the compound-symmetry structure. The estimate for the concentration coefficient will be reported, including standard error, degrees of freedom and 95% confidence interval for the coefficient. The concentration effect model will be fit using the PK analysis set. The SAS code for this analysis can be found in the TFL shells.

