311	Important	Withdrawal Criteria	Observable	Discontinuation of M8891 is desired or considered necessary by the Investigator and/or the subject (if applicable) due to occurrence of > Grade 2 AEs for more than 6 days but subject not withdrawn from M8891 treatment	Source Data Review	
312	Important	Withdrawal Criteria	Observable	Subject experienced a DLT and was not withdrawn from the trial therapy.	Source Data Review	
313		Withdrawal Criteria	Programmable	Occurrence of pregnancy but subject was not removed from the trial therapy	Off-Line Manual Listing	
400	Important	AE/SAE	Observable	Safety Reports (SAE, IND) not reported to IRB as required. Safety Reports (SAE,	Source Data Review	
401	Important	AE/SAE	Observable	IND) not reported to EMD-GPS within 24 hours of event.	Source Data Review	
402	Important	AE/SAE	Observable	Pregnancies considered by the Investigator to be related to trial treatment resulting from a drug interaction with a contraceptive medication are not reported as an AEs.	Source Data Review	
500	Important	Visit Schedule	Programmable	Missing data for Physical Examination.	On-Line Check Off-Line Manual Listing	
501	Important	Visit Schedule	Programmable	Missing data for Vital signs.	Off-Line Manual Listing	
503	Important	Visit Schedule	Programmable	Missing data for pregnancy testing for Female subjects of Childbearing potential. Missing data for	On-Line Check	
505	Important	Visit Schedule	Programmable	Pharmacokinetic Blood sampling.	On-Line Check	Yes
531	Important	Visit Schedule	Programmable	ECG assessment is missing for "/timepoint/, /record #/".	Off-Line Manual Listing	

PD REF ID	Category (DVCAT)	Classification (DVDECOD)	Type of Deviation Observable/ Programmable (Data Driven)	PD (DVTERM	PD Identification Method Options	cIPD ?
554	Important	Visit Schedule	Observable	A minimum of 7 days laps not achieved between dosing of subject 1 and subsequent subject in each cohort without SMC approval.	Source Data Review	
547	Important	Visit Schedule	Observable	Screening assessment dates are not within 28 Days prior to informed consent for a subject that has been re-screened.	Source Data Review	
600	Important	IP Admin/Study Treat	Observable	Subject received / has taken wrong dose / treatment schedule of M8891 different from the planned for the subject.	Source Data Review	

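### The PK analysis set excludes by subject, not by profile, so a major PK-affecting problem on one day takes valid profiles on other days out of the summaries and models

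*Protocol*

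**What the plan says.** Table 13 (Protocol 8.4) and Table 1 (SAP 8.2) define the PK set with the same opening sentence: "All subjects from the safety analysis set without major protocol deviations/violations or events that would affect PK". Both add a sufficiency rule: "Sufficient concentration data is defined as at least 3 valid, post-dose concentration points in the PK profile to obtain any PK parameter". Neither has a clause that excludes a single day or profile. SAP 10.2.2 counts and lists exclusions by subject and population.

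The analysis itself runs by day. Protocol 8.5.4.1 describes PK variables for each dose level and day separately, then states: "All analyses will be based on the PK data set". SAP 16.1.1 and 16.1.3 use this set for mean concentrations and for parameter summaries, and SAP 16.1.4 uses it for the dose-proportionality regression. SAP 15.7 adds: "The concentration effect model will be fit using the PK analysis set".

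Two further statements bear on size. Protocol 5.1.3.1 says of Part 1: "Sequential cohorts of 3 subjects at the same dose level will be used". SAP 9.2 says of concentration summaries: "If there are fewer than 3 observations, only N, Min, and Max will be reported".

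**The concern.** The unit of exclusion does not match the unit of analysis. Vomiting on Day 15 says nothing about a Day 1 profile that was already complete. Nor does a combined CYP inhibitor started after Day 1. SAP 18.1 item 700 flags use of such inhibitors during treatment as clinically important and does not say when in treatment the use has to fall. Under the literal rule the subject leaves the set, and the sound Day 1 profile leaves with the spoiled one.

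Three things are at stake: the precision of the day-specific PK summaries, the number of points in the dose-proportionality fit, and the paired concentration and ECG data in the QTcF model. With few subjects per dose level, each lost profile counts. Table 13 also covers Part 2A, so the same membership rule would apply to the Day -1 fed profile if a later day were spoiled.

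**Working it through.** **Inputs from the documents**
- Part 1 planning scenario (Protocol 8.1.1): five dose levels of 3 subjects, two of 6, one of 9. Check: 5×3 + 2×6 + 1×9 = 36, which matches the stated 36 evaluable subjects. So 5 of 8 levels have only 3.
- Full PK days in Part 1: Cycle 1 Day 1 and Day 15 (Table 1, footnote m).
- Minimum number of concentrations for a mean: 3 (SAP 9.2).

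**Direct consequence.** A 3-subject level that loses one subject has 2, which is below 3. Under subject-level exclusion this holds on both days. Under profile-level exclusion it holds only on the affected day, which loses its mean under either rule. The avoidable loss is therefore the other day.

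**Illustration of size.** Let q be the chance that a given subject's given PK day is spoiled by a major PK-affecting deviation or event, independent across days and subjects. The documents give no such rate, so q is an assumption, shown from 2% to 20%.
- Subject-level rule: a subject stays with probability (1−q)², and all three must stay. P(fewer than 3 on a given day) = 1 − (1−q)⁶.
- Profile-level rule: P = 1 − (1−q)³.

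| q | Subject-level | Profile-level |
|---|---|---|
| 2% | 11.4% | 5.9% |
| 5% | 26.5% | 14.3% |
| 10% | 46.9% | 27.1% |
| 20% | 73.8% | 48.8% |

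Worked case, q = 10%: 1 − 0.9⁶ = 1 − 0.531 = 0.469, and 1 − 0.9³ = 1 − 0.729 = 0.271. Over the five 3-subject levels, the expected number without a concentration mean on a given day is 5 × 0.469 = 2.3 against 5 × 0.271 = 1.4.

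**Larger levels.** At q = 10% under the subject-level rule, each subject stays with probability 0.9² = 0.81. The binomial chance that fewer than 3 of 6 stay is 1.4%; for 9 subjects it is under 0.1%. These levels are nearly immune to losing the mean, although they can still lose valid profiles.

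**Sensitivity to independence.** If every cause affected both days of a subject together, a subject would be lost with probability q under either rule, and both columns would equal 1 − (1−q)³. The gap is largest for one-day problems and vanishes for fully persistent ones.

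**The case against.** The case against is that the plan has safeguards and the loss is limited.

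- **Only major problems count.** A reader might infer that any deviation removes a subject. The text does not support this: the deviation must be major and affect PK, and SAP 8.1 leaves the final decision on deviations to the data review meeting. Out-of-window samples already have sample-level handling (SAP 16.1.1). This narrows the trigger. It does not supply a day-level option, and SAP 8.1 speaks of deviations, not of events such as vomiting.
- **Missing samples are not an automatic trigger.** SAP 18.1 item 505 (missing data for "Pharmacokinetic Blood sampling") is marked clinically important, so a reader might infer that gaps on Day 15 remove Day 1. But one profile with 3 valid post-dose points meets the sufficiency rule, and the mark may mean only that key objectives could be affected. This objection stands.
- **Nothing is deleted.** Listings and individual profile plots use the safety population and flag excluded subjects (SAP 16.1.1, 16.1.3). This stands. The loss is from summaries and models.
- **Parameters are still summarised.** SAP 9.2 sets its minimum of 3 for concentrations and states none for parameters such as Cmax and AUC. This stands too: at 2 subjects those summaries get thinner but do not disappear.
- **Day-level reliability.** SAP 16.1.2 calculates parameters for Day 1 and Day 15 when reliable. That governs calculation, not membership of the set.

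**Conclusion.** The point holds in limited form. Followed literally, both tables remove valid profiles on unaffected days from the PK summaries and the two models, and no passage gives a day-level rule for major PK-affecting deviations or events. In 3-subject levels of Part 1, this also costs the mean concentration on the unaffected days. The avoidable increase in the chance of falling below 3 on a given day is about 12 percentage points at q = 5% (26.5 − 14.3) and about 20 at q = 10% (46.9 − 27.1). These figures rest on an assumed q, on independence and on two full PK days, so they illustrate the size and do not estimate it.

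Two wider readings are not supported. A reader might infer harm to dose decisions by the Safety Monitoring Committee, but SAP section 4 places those analyses in a separate plan that is not available here. A reader might also infer that Part 2A loses its mean concentrations. The SAP was written for the monotherapy escalation, the protocol states no minimum for a mean, and nothing carries the minimum of 3 over to Part 2A. All analyses are descriptive, and the DLT analysis uses a different set, so no primary conclusion is at risk.

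**What to change.** In Protocol Table 13 and SAP Table 1, keep a treated subject in the PK set if at least one profile is evaluable. Apply major PK-affecting deviations and events by profile (subject by PK day) or by sample. Exclude only the affected data from summaries and models, and flag them in the listings.

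The cost is one sentence in each table and a day-level exclusion flag in the PK dataset. The downside is small: N may differ by day within a dose level, so each table should show N for its day.

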8.5 Description of Statistical Analyses

8.5.1 General Considerations

The following summary statistics will be used to summarize the trial data per Part and dose level unless otherwise specified:

- Continuous variables: number of not missing observations, mean, standard deviation, median, minimum, and maximum
- Categorical variables: frequencies and percentages.

All summary statistics will be described in detail in the respective Integrated Analysis Plan. There is no formal significance level for this trial and all analyses are considered descriptive.

The cutoff for the analysis will be as follows:

For the analysis after the end of Part 1, the cutoff will be Last Subject Last Visit (LSLV), or 4 months after the last subject enrolled into the monotherapy dose escalation cohort has finished their DLT period, whichever comes first.

For both dose escalation parts, the analysis will focus on the number of subjects experiencing a DLT. The SMC will receive results of a Bayesian two-parameter logistic model with overdose control updated with the observed DLT data for SMCs dedicated to dose escalation decisions ([Babb 1998; Neuenschwander 2008](#)). Recommendation is based on a loss function (probabilities of being in one of the four toxicity probability intervals will be multiplied with a loss term as follows:

$$0 * P(\text{target dosing (0.17-0.33)}) + 1 * P(\text{for over (0.33-0.67] or under dosing [0-0.17]}) + 2 * P(\text{excessive dosing (0.67-1]}).$$

Glossary:

(x.xx-y.yy] = lower limit excluded, upper limit included in the penalties
[x.xx-y.yy] = lower limit included, upper limit included in the penalties

In addition, only doses that have a corresponding probability of less than 25% that the true DLT rate is more than 33% (overdose control) are recommended by the model. The recommended dose level from the Bayesian model for the next cohort is the dose with the lowest loss function from all doses fulfilling the overdose control rule.

- MTD definition

The target DLT rate for the MTD definition is 30%. The MTD suggested by the model (if reached) will be defined as follows:

Highest tested dose with estimated DLT rate $\leq 30\%$. Additionally, the following needs to be fulfilled:

- The upper bound of the 95% credible interval of a potential MTD is not more than 40% and
- The estimated DLT probability for the suggested MTD is above or equal to 17%.

The SMC will be notified of a potential MTD if a tested dose fulfills the above last 2 criteria. The SMC defines the MTD and can deviate from the suggestion of the model.

